radiotherapy, presence/absence of baseline intracranial metastasis, use of concomitant drugs, or personal clinical history of psychiatric/mood diseases⁶. However, limited data are available about the occurrence of CNS AEs when lorlatinib is used in the first line of treatment (local approval in Spain February 2023) in a real-world population.

On the other hand, lorlatinib has proved its efficacy and safety in clinical trials, but real-world evidence is needed to confirm these results in wider patient populations and to identify prognostic and predictive factors not captured in clinical trials. Ethnicity, molecular variants, and circulating tumour DNA (ctDNA) clearance may influence treatment outcomes and require personalized or combinational approaches.

Research question and objectives

Research question

 What is the spectrum of adverse events and mitigation strategies associated with lorlatinib as a first line treatment in an ALK+ NSCLC real-world Spanish population?

Primary Objective

 To describe all the spectrum of the adverse events (AEs) of Lorlatinib (CTCAE v6.0) and its mitigation strategies, with special interest in CNS AEs

Secondary Objectives

- To identify factors that are predictive of AEs, with special interest in CNS AEs
- To evaluate the effectiveness of 1L lorlatinib in real-world practice
 - 1. rwPFS rate at 12 and 18 months in the ITT population with and without brain metastasis at baseline
 - 2. rwDuration of Response (DoR)
 - 3. rwDuration of Treatment (DoT)
 - 4. rwTime to next therapy/treatment (TTNT)
 - 5. rwSystemic and intracranial Objective Response rate (ORR) using Response Evaluation Criteria in Solid Tumors (RECIST) v1.1. criteria
 - 6. rwTime to intracranial progression rate at 12 and 18 months with and without brain metastasis at baseline
 - 7. rwCumulative incidence of brain metastases (BM) in ITT population at 12 and 18 months (with and without baseline BM)

- 8. rwOverall survival (OS) rate at 12 and 18m
- To evaluate the impact of lorlatinib on patients' quality of life
- To describe ALK testing methods used

Exploratory Objectives (up to 30 patients)

 To identify neuroimaging markers (Magnetic Resonance Imaging; MRI) that are predictive of the occurrence of CNS AEs

Study Design

The study is an observational, non-interventional, prospective and multicenter trial that evaluates the real-world safety and effectiveness of lorlatinib as a first-line treatment in patients with ALK-positive advanced NSCLC in Spain.

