permanent treatment interruption in eight patients (5%), which happened in the first 26 months. With crizotinib, 15% of patients had dose reduction, 48% had temporary treatment interruption, and 11% had permanent discontinuation because of AEs from any cause.

Solomon et al reported lorlatinib is associated with neurologic toxicity (mood/speech and cognitive areas), accounting for 35% of patients in the CROWN trial (3yr follow up of the pivotal trial⁸), being in most patients grade 1. CNS AEs did not have a negative impact on patient-reported quality of life. Most CNS AEs resolved (33% without intervention and 17% with lorlatinib dose modification), while 38% were unresolved; most required no intervention. Lorlatinib dose modification did not influence PFS. Few observational studies have reported the frequency of CNS toxicity on patients with ALK+ NSCLC receiving lorlatinib, however no information is available regarding patients from South Europe. The study will be relevant to learn more about the frequency in our population and about the clinical management in real clinical practice.

Lorlatinib also had a manageable safety profile, with hyperlipidemia, weight gain, and hypertension being the most common G3/4 adverse events and some others with lower frequency as the alterations at the CNS level (mood/speech and cognitive) that generate some uncertainties regarding an adequate management. Occurrence of adverse events with lorlatinib in Spain (2nd and later lines approval in February 2021) is known in later lines of treatment and it seems that several factors involved in that previously treated population (use of radiotherapy, presence/absence of baseline intracranial metastasis, use of concomitant drugs, personal clinical history of psychiatric/mood diseases, etc.) are associated to certain types of AEs, i.e. the CNS adverse events⁶, but the occurrence of those AEs are not well-known with the use of the drug in the first line of treatment (local approval February 2023) and that is one of the reasons why this data gap with lorlatinib should be covered.

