8. RESEARCH QUESTION AND OBJECTIVES

Research question

 What is the spectrum of adverse events and mitigation strategies associated with lorlatinib as a first line treatment in an ALK+ NSCLC real-world Spanish population?

Primary Objective

• To describe all the spectrum of the adverse events (AEs) of Lorlatinib (CTCAE v6.0) and its mitigation strategies, with special interest in CNS AEs

Secondary Objectives

- To identify factors that are predictive of AEs, with special interest in CNS AEs
- To evaluate the effectiveness of 1L lorlatinib in real-world practice
 - 1. rwPFS rate at 12 and 18 months in the ITT population with and without brain metastasis at baseline.
 - 2. rwDuration of Response (DoR)

- 3. rwDuration of Treatment (DoT)
- 4. rwTime to next therapy/treatment (TTNT)
- 5. rwSystemic and intracranial Objective Response rate (ORR) using Response Evaluation Criteria in Solid Tumors (RECIST v1.1.) criteria
- 6. rwTime to intracranial progression rate at 12 and 18 months with and without brain metastasis at baseline
- 7. rwCumulative incidence of brain metastases (BM) in ITT population at 12 and 18 months (with and without baseline BM)
- 8. rwOverall survival (OS) rate at 12 and 18m
- To evaluate the impact of lorlatinib on patients' quality of life
- To describe ALK testing methods used

Exploratory Objectives (up to 30 patients)

• To identify neuroimaging markers (MRI) that are predictive of the occurrence of CNS AEs

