9. RESEARCH METHODS

9.1. Study Design

This is an observational, non-interventional, prospective, multicenter and nationwide study with the category of PASS (Post Authorization Safety Study), which seeks to answer the research question: what is the spectrum of adverse events and mitigation strategies associated with lorlatinib in a real-world Spanish population? For this purpose, an observational, non-interventional and prospective study design is ideal to faithfully reflect what occurs in the routine clinical practice.

It is important to note that our study population exhibits a low incidence of NSCLC patients, approximately 3-4%. Consequently, the current study is descriptive in nature, as it lacks the statistical robustness (relatively small sample, but almost similar to the total of patients included in the pivotal trial) necessary to establish a significant association between a specific adverse event and the drug.

The primary objective will be to describe all the spectrum of the AEs of Iorlatinib (CTCAE v6.0) and its mitigation strategies with special interest in CNS AEs.

Primary Objective	Corresponding Endpoint			
To describe all the spectrum of the adverse events (AEs) of Lorlatinib (CTCAE v6.0) and its mitigation strategies, with special interest in CNS AEs	Occurrence (number of adverse events) and severity of AEs, with severity determined according to NCI CTCAE v6.0 criteria. Frequency and period of dose reductions as well as concurrent medications used to control AEs will be collected			
Secondary Objectives	Corresponding Endpoints			
To identify factors that are predictive of AEs, with special interest in CNS AEs	To evaluate the relationship of multiple demographic and clinical factors with the incidence of AEs, with special interest in CNS adverse events			
To evaluate the effectiveness of 1L lorlatinib in real-world practice	• Effectiveness will be assessed:			
rwPFS rate at 12 and 18 months in the ITT population with and without brain metastasis at baseline	1. To determine real-world progression-free survival (rwPFS) defined as the time from enrollment to the first occurrence of disease progression (intracranial or systemic) or death from any cause, whichever occurs first, as determined by the investigator using RECIST v1.1. criteria, at 12 and 18 months, in the ITT population with and without brain metastasis at baseline			

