- 1. **Baseline visit:** the day on which the patient fulfils the inclusion and exclusion criterion, including signature of the Informed Consent (i.e. the day on which the prospective observation starts) (within cycle 1 if lorlatinib)
- 2. Follow-up visit 1: will be scheduled at month 3 (third cycle of Iorlatinib)
- 3. Follow-up visit 2: will be scheduled at month 6 (sixth cycle of Iorlatinib)
- 4. Follow-up visit 3: Follow-up visit at month 12 (twelfth cycle of lorlatinib)
- 5. Final Visit: end of follow-up (end of data collection expected November 2027)

Data collection overview

Study Visits and Assessments	Baseline			FU3 C12D1	Final Visit
Informed consent	X				
SOCIO DEMOGRAPHIC DATA					
Medical history	X				
Physical examination including Height and weight	X	X	X	X	X

Study Visits and Assessments	Baseline	FU1	FU2	FU3	Final
		C3D1	C6D1	C12D1	Visit
Previous personal and family history of cancer	X				
CLINICAL DATA					
ECOG	X	X	X	X	X
Laboratory: Hematology and Blood chemistry (dyslipemia profile included). According to routine clinical practice	X	X	X	X	X
Comorbidities since Index Date: Charlson Index	X	X	X	X	X
Concomitant treatment(s) including previous history of Thromboembolic Disease	X	Х	X	X	X
Information of baseline tumor diagnosis: date, staging, (TNM),biopsy, PD-L1 expression, other mutations, etc	X				
Information regarding advanced disease: date, staging, metastatic location, CNS metastasis, previous systemic chemotherapy, radiotherapy, etc	X				
Previous systemic chemotherapy (Yes/No)	X				
Assessments CT scan	X				
Assessments brain MRI	X				
LORLATINIB TREATMENT					
Start, Stop and Discontinuation date	X	X	X	X	X
Dose by cycle	X	X	X	X	X
Reason for discontinuation or for dose reduction	X	X	X	X	X
Evaluation of Treatment Response: method (CT scan, MRI, others) and response	х	Х	X	X	X
AFTER LORLATINIB TREATMENT					

Study Visits and Assessments		FU1	FU2	FU3	Final
		C3D1	C6D1	C12D1	Visit
Post-progression treatment: type and palliative care					X
Date of death or last follow-up or last contact					X
QUALITY OF LIVE					
EORTC QLQ C30, LC13	X	X	X	X	X
SAFETY					
PRO-CTCAE	X	X	X	X	X
Adverse Events	X	X	X	X	X

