Variable	Role	Data source(s)	Operational definition
Height at treatment initiation	Baseline patient's characteristics	Investigators Patient clinical record/Electronic Health record (EHR)	• Meters
Weight at treatment initiation (and usual weight prior to diagnosis)	Baseline patient's characteristic	Investigators Patient clinical record/Electronic Health record (EHR)	• Kg
Clinical data prior to the	ne start of trea	tment with lorlati	nib
Patient's clinical situation Performance status before the start of treatment lorlatinib by Eastern Cooperative Oncology Group (ECOG)	characteristics	Investigators Patient clinical record/Electronic Health record (EHR)	Baseline autonomy status of the patient by Eastern Cooperative Oncology Group (ECOG)
Baseline Relevant comorbidities (Yes / No) Charlson Comorbidity Index	Baseline patient's characteristics	Investigators Patient clinical record/Electronic Health record (EHR)	 Lack of co-morbidity: 0-1 Low comorbidity: 2 High Comorbidity: >=3
Past personal or family history of psychiatric or neurological conditions	Baseline patient's characteristic	Investigators Patient clinical record/Electronic Health record (EHR)	Yes/No
Relevant concurrent medications:	Baseline patient's characteristics	Investigators Patient clinical record/Electronic Health record (EHR)	 Neurotropic, Psychiatric and mood medication Anticonvulsants Other

Variable	Role	Data source(s)	Operational definition
Previous history of Thromboembolic Disease	Baseline patient's characteristics	Investigators Patient clinical record/Electronic Health record (EHR)	• Yes/No
embolic origin, regardless	characteristic	Investigators Patient clinical record/Electronic Health record (EHR)	Thrombotic/embolic
Events of thrombotic or embolic origin, regardless	characteristic	Investigators Patient clinical record/Electronic Health record (EHR)	Superficial / deep
emlic origin, regardless	Baseline patient's characteristic	Investigators Patient clinical record/Electronic Health record (EHR)	• Yes/No

Variable	Role	Data source(s)	Operational definition
Information of baseline tumor diagnosis Date of first diagnosis. It is considered the first diagnosis as the first record in the confirmatory clinical history of the presence of tumor lesion by biopsy.	patient's characteristics	Investigators Patient clinical record/Electronic Health record (EHR)	Date format

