9.5. Study Size

In the CROWN trial, the incidence of CNS AEs was 42%⁴ and we assumed that the incidence could be higher in the real clinical practice, but it is under detected as most cases are grade 1. We estimated that we need 116 ALK+ NSCLC patients with an 80% power to detect an incidence of 55% any grade CNS AEs using a 2-sided test. We expect that the recruitment will be completed over a period of one and a half years, as described in the study schedule at 20 sites countrywide.

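### Section 9.3 records personal psychiatric/mood history, one of several CNS AE risk factors named in the rationale, only inside a single Yes/No that also covers family and neurological history

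*Protocol*

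**What the plan says.** Section 8 gives as the first secondary objective "To identify factors that are predictive of AEs, with special interest in CNS AEs". The endpoint table in Section 9.1 turns this into "To evaluate the relationship of multiple demographic and clinical factors with the incidence of AEs".

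The background says which factors have been linked to CNS AEs when lorlatinib follows other ALK inhibitors. The Abstract (Section 4) lists prior brain radiotherapy, baseline intracranial metastasis, concomitant drugs and "personal clinical history of psychiatric/mood diseases". Section 7 repeats the list, ending with "use of concomitant drugs, personal clinical history of psychiatric/mood diseases, etc".

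In Section 9.3, under clinical data before the start of lorlatinib, the corresponding row is "Past personal or family history of psychiatric or neurological conditions", and its operational definition is Yes/No. The row has no sub-item for whose history it is or what kind of condition. A neighbouring row on concurrent medication has the category "Neurotropic, Psychiatric and mood medication". The visit table in Section 9.2 has a baseline row "Medical history" for which no psychiatric item is defined.

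**The concern.** The background's factor is personal and psychiatric/mood. The variable collected is personal or family, and psychiatric or neurological. A patient with past major depression and a patient whose parent had a stroke both score Yes.

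A mismatch of this kind differs from an analysis detail left open. An SAP can choose a model, but it cannot split one recorded bit into four histories. At stake is whether the study can say anything specific about one of the factors its own rationale puts forward, even in a simple descriptive table of CNS AEs by personal psychiatric/mood history.

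**Working it through.** **Plan's own figure.** The only design figure is N = 116 for a CNS AE incidence of 55% against 42%, two-sided, 80% power (Section 9.5). Alpha is not stated; 0.05 is assumed. Arcsine formula: h = 2·asin(√0.55) − 2·asin(√0.42) = 1.6710 − 1.4101 = 0.2609, and n = (1.960 + 0.842)²/h² = 115.3, so 116. The figure reproduces. It sizes the overall incidence and does not bear on this point.

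**Named factors against collected variables.**

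| Factor in the background | Variable in Section 9.3 |
|---|---|
| Prior brain radiotherapy | Whole-brain radiation and radiosurgery, separate rows |
| Baseline intracranial metastasis | Brain metastases at lorlatinib start, own row |
| Concomitant drugs | Concurrent medication, with a psychiatric/mood category |
| Personal psychiatric/mood history | Merged row only |

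Only the last factor loses its identity at entry.

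**What merging does.** Let p be the share with personal psychiatric/mood history, q the share of the remaining patients who are Yes only for another history, d1 the excess CNS AE risk of the first group over the No group, and d2 that of the second. The share of Yes answers that are personal psychiatric/mood is w = p/[p + (1 − p)q]. The recorded risk difference is w·d1 + (1 − w)·d2. Every input below is an assumption; the Protocol gives none of them.

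*Other histories carry no extra risk (d2 = 0).* Take 65% risk with personal history and 40% without, so d1 = 25 points and the true risk ratio is 1.63.
- p = 0.10, q = 0.40: w = 0.10/0.46 = 0.217. Risk in Yes = (0.065 + 0.144)/0.46 = 0.454. Difference 5.4 points, risk ratio 1.14.
- p = 0.20, q = 0.20: w = 0.20/0.36 = 0.556. Risk in Yes = (0.130 + 0.064)/0.36 = 0.539. Difference 13.9 points, risk ratio 1.35.

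*Other histories carry half the excess (d2 = 12.5 points).* The recorded difference is 5.4 + 0.783 × 12.5 = 15.2 points, or 13.9 + 0.444 × 12.5 = 19.4 points. Dilution shrinks.

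*Other histories carry all the excess (d1 = 0, d2 = 25 points).* The recorded difference is 0.783 × 25 = 19.6 points, or 0.444 × 25 = 11.1 points, with no psychiatric effect at all. With w = 0.556, a purely psychiatric effect shows 13.9 points and a purely non-psychiatric one 11.1. The merged field can hardly tell them apart.

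**Effect on power at N = 116.** Assume overall incidence 55%, p = 0.15, d1 = 25 points, d2 = 0. Risk without the history is 0.55 − 0.15 × 0.25 = 0.5125 and with it 0.7625, an odds ratio of 3.05. Two-proportion normal test, two-sided 0.05:

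| Field | Share Yes | Odds ratio | Power |
|---|---|---|---|
| Separate | 15% | 3.05 | about 49% |
| Merged, q = 0.10 | 23.5% | 1.95 | about 30% |
| Merged, q = 0.20 | 32% | 1.62 | about 21% |
| Merged, q = 0.30 | 40.5% | 1.46 | about 16% |

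Over p = 10–20%, d1 = 25–30 points and q = 10–30%, power is 35–77% with a separate field and 10–55% with the merged one.

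**The case against.** The strongest reply is that Section 9.3 is not the eCRF. Section 9.6 describes a specially designed eCRF, which is not shown. Section 9.3 also condenses elsewhere, for example personal and family cancer history in one row. The baseline medical history row, or the source record, might hold the detail. This stands as a limit: loss of the information is inferred from the definition, not documented. But no psychiatric item is defined anywhere else, and Section 9.3 confines documentation to routine-practice variables that follow the objectives. An eCRF built as written would carry the merged field.

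A reader might infer that this is the key predictor of CNS AEs, or that the merged field defeats the secondary objective. The documents do not support that. The factors are listed unranked, this one among several, and the others have their own fields. The first-line gap stated in the background concerns how often these AEs occur; the Protocol promises an open search for predictors, not a test of psychiatric history in particular.

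A reader might also infer that the study will wrongly report no association. That requires the other histories to carry little or no extra risk, which nothing in the Protocol states.

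Baseline psychiatric/mood medication does identify patients under current treatment, so the factor is not wholly invisible. It misses past or untreated illness.

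Finally, the study calls itself descriptive, and power would be modest even with a separate field. That limits the gain from the fix, but the descriptive table needs the separate field just as much as a model does.

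**Conclusion.** The point holds in a limited form. Section 9.3 fixes a definition that does not match the factor named in Sections 4 and 7. If the eCRF follows it, the association of personal psychiatric/mood history with CNS AEs cannot be isolated: diluted if the other histories carry less risk, not attributable if they carry risk too. This rests on the text and needs no assumed figure.

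The size is not established. The illustrative figures depend on assumed risks and prevalences, and the dilution figures also on no extra risk from family or neurological history. The rest of the predictor objective is unaffected. The change is worth making because it is cheap at the design stage and may be impossible once data are collected.

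**What to change.** In Section 9.3 and the baseline eCRF page, record personal psychiatric/mood history as its own Yes/No/Unknown item. Keep it separate from personal neurological history and from family history, with the latter split into psychiatric and neurological. An Unknown option matches the coding that Section 9.3 already uses for asbestos exposure and cancer history.

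The full split adds three tick boxes, filled from the same records and with no added procedure. Separating personal psychiatric/mood history alone would meet the main need. Which predictor, if any, is pre-stated for CNS AEs can be settled in the SAP. If the eCRF already separates these histories, aligning the Section 9.3 row with it is enough.

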2. rwDuration of Response (DoR)	2. To determine real world duration of response (DOR), as the time from the first occurrence of a documented objective response to disease progression or death from any cause, whichever occurs first, as determined by the investigator according to RECIST v1.1. criteria (or Time from first documentation of CR or PR (whichever occurs first) after index until death or PD)			
3. rwDuration of Treatment (DoT)	3. To determine duration of treatment (DoT) as the time from lorlatinib's first dose to last dose for any cause. (Time to treatment discontinuation or Time from first dose to last dose of a treatment)			

4.	rwTime to next therapy/treatment (TTNT)	4.	To determine Time to next therapy/treatment (TTNT) as the Time from end of lorlatinib treatment to institution of next therapy	
5.	rwSystemic and intracranial Objective Response rate (ORR) using RECIST v1.1. criteria.	5.	To determine the systemic and real-world intracranial objective response rate (ORR) as determined by the investigator using RECIST v1.1. criteria	
6.	rwTime to intracranial progression rate at 12 and 18 months with and without brain metastasis at baseline	6.	Real world Time to intracranial progression rate at 12 and 18 months with and without brain metastasis at baseline	
7.	rwCumulative incidence of brain metastases (BM) in ITT population at 12 and 18 months (with and without baseline BM)	7.	Real world Cumulative incidence of brain metastases (BM) in ITT population at 12 and 18 months (with and without baseline BM)	
8.	rwOverall survival (OS) rate at 12 and 18m	8.	To determine the real-world overall survival (OS) rate at 12 and 18 months. OS is defined as the time from enrollment to death from any cause	
To evaluate the impact of lorlatinib on patients' quality of life.		of Pl Lo ar	hange from baseline in health-related quality f life (HRQoL), using the EORTC C30, RO_CTCAE (for CNS AEs) and submodules C13 at baseline, C1D15, C2D1, C3D1, C6D1 and every 3 months until the 1st year and then very 6 months	
To describe ALK testing methods used		Describe the different methods used to testing ALK mutations		
Exploratory Objectives (up to 30 patients)			Corresponding Endpoints	
To identify neuroimaging markers (MRI) that are predictive of the occurrence of CNS AEs		Fazekas scale, morphometric and radiomic analysis of baseline magnetic resonance images (MRIs) to identify imaging markers associated with the development of CNS AEs		

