Tumor staging at diagnosis	patient's characteristics	Investigators Patient clinical record/Electronic Health record (EHR)	International TNM Staging system
Tumor staging at the study initiation	patient's characteristics	Investigators Patient clinical record/Electronic Health record (EHR)	International TNM Staging System
Histological classification	patient's characteristics	Investigators Patient clinical record/Electronic Health record (EHR)	According to World Health Organization Guidelines (WHO Lung cancer 2023).
ALK rearrangement Tested:	patient's characteristics	Investigators Patient clinical record/Electronic Health record (EHR)	• Yes/No
ALK Method	patient's	Investigators Patient clinical record/Electronic	(IHC/FISH/NGS/RNASeq /NanoString/Others: Specify

Variable	Role	Data source(s)	Operational definition
		Health record (EHR)	
ALK Result	characteristics	Investigators Patient clinical record/Electronic Health record (EHR)	Positive/Negative/ Unknown) per each test
If NGS was performed:	characteristics	Investigators Patient clinical record/Electronic Health record (EHR)	ALK fusion partner and EML4 variant, co- occurrence of TP53 mutations
PD-L1 expression	ala ana atamiatia a	Investigators Patient clinical record/Electronic Health record (EHR)	Tested: Yes/NoIHC Test:Result (% TPS)
Additional mutational findings:	characteristics	Investigators Patient clinical record/Electronic Health record (EHR)	 ALK fusion variant ctDNA tumor fraction TP53 mutational status KRAS/BRAF/MAPK/ PI3K/mTOR, RTK, or cell cycle pathway aberrations. TMB
Information regarding advanced disease Date of first diagnosis (de novo or relapse in early stages).	characteristics	Investigators Patient clinical record/Electronic Health record (EHR)	The first diagnosis is considered as the first record in the confirmatory clinical history of the presence of the disease
Diagnosis of stage IV disease (Yes/No)	habaraatariatiaa	Investigators Patient clinical record/Electronic	The first diagnosis is considered as the first record in the confirmatory clinical history of the

Variable	Role	Data source(s)	Operational definition
		Health record (EHR)	presence of metastatic tumor lesion
Type of metastatic locations (check all that apply)	patient's characteristics	Investigators Patient clinical record/Electronic Health record (EHR)	• Locations
Brain metastasis at diagnosis	patient's characteristics	Investigators Patient clinical record/Electronic Health record (EHR)	• (Yes/No/Unknown)

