Imaging method for brain metastasis screening	patient's characteristics	Investigators Patient clinical record/Electronic Health record (EHR)	• (CT/MRI/None/Unknown)
Brain metastases present at time of lorlatinib initiation	patient's characteristics	Investigators Patient clinical record/Electronic Health record (EHR)	• Yes/No
Previous treatments for brain metastasis	patient's characteristics	Investigators Patient clinical record/Electronic Health record (EHR)	 Concomitant steroid treatment (Yes/No) Symptomatic (Yes/No) List

Variable	Role	Data source(s)	Operational definition
Surgery	Baseline patient's characteristics	Investigators Patient clinical record/Electronic Health record (EHR)	Yes/No. Date
Whole brain radiation Yes/No (Date of last dose)	Baseline patient's characteristics	Investigators Patient clinical record/Electronic Health record (EHR)	• (Date of last dose)
SRS/radiosurgery	Baseline patient's characteristics	Investigators Patient clinical record/Electronic Health record (EHR)	Yes/No (Date of last dose
Has the patient participated in a clinical trial previously?	Baseline patient's characteristics	Investigators Patient clinical record/Electronic Health record (EHR)	• (Yes/No/Unknown)
Previous radiotherapy	Baseline patient's characteristics	Investigators Patient clinical record/Electronic Health record (EHR)	• (Yes/No)
Intention of previous radiotherapy	Baseline patient's characteristics	Investigators Patient clinical record/Electronic Health record (EHR)	Curative, palliative

Variable	Role	Data source(s)	C	perational definition
Location of previous curative radiotherapy	Baseline patient's characteristics	Investigators Patient clinical record/Electronic Health record (EHR)	•	Chest, bone, brain, others (specify
Previous systemic chemotherapy	Baseline patient's characteristics	Investigators Patient clinical record/Electronic Health record (EHR)	•	Yes/No
Previous systemic chemotherapy Intention	Baseline patient's characteristics	Investigators Patient clinical record/Electronic Health record (EHR)	•	Curative (adjuvant or neoadjuvant)
Previous systemic chemotherapy Regimen used	Baseline patient's characteristics	Investigators Patient clinical record/Electronic Health record (EHR)	•	List
Clinical data during t	reatment with le	orlatinib		
Start and end of treatment	notiont's	Investigators Patient clinical record/Electronic Health record (EHR)	•	Date from the first lorlatinib treatment taken and last

Variable	Role	Data source(s)	Operational definition

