The study will capture results/data only from procedures that were actually performed as part of a participant's routine medical care, as determined by their treating physician.

Imaging analysis^{12,13}

Brain MRI will be collected at baseline and in case of CNS toxicity. Images will be anonymized and shared to assess Fazekas scale, morphometric and radiomic features that will be correlated with CNS toxicity.

The Fazekas scale will be calculated from the baseline MRI images of each patient. We will qualitatively evaluate the presence of White Matter hyperintensities on FLAIR images using a 4-point rating scale. Specifically, the assigned values for this rating scale were: 0 for no lesions, 1 for focal lesions, 2 for beginning confluence of lesions, and 3 for diffuse involvement of the entire regions with or without the involvement of U fibers.

The morphometric analysis will be completed by studying the volumetry of brain structures, including gray matter, white matter, and cerebrospinal fluid, which will also allow us to define the total intracranial volume. The morphometric analysis will be conducted using the SPM12 software (Welcome Department of Imaging Neuroscience Group) running on MATLAB (Mathworks). In patients with brain metastases at baseline, each of the lesions will be identified and delineated using T1-gadolinium and FLAIR (fluid-attenuated inversion recovery) utilizing the image analysis sequences, free software **MRIcron** (http://www.mccauslandcenter.sc.edu/mricron/mricron). The contrast-enhancing identified in the T1-gadolinium sequence will be defined as the tumor masks (ROI - region of interest). Similarly, the areas outlined in the FLAIR sequence will define the tumor edema compartment. In an initial analysis, the number of lesions, volumetric data (mm³) for each lesion, and the total sum of all lesions per patient will be calculated, as well as the tumor/edema ratio for each lesion and the sum of all lesions. We will perform an exploratory radiomics analysis, leveraging the masks (ROIs) previously defined in the morphometric analysis. After delineating the ROIs in the previous analysis, several variables related to texture and edge descriptors will be extracted. Weighted averages of each radiomics variable will be obtained for patients with more than one metastatic lesion. These averages will be weighted by the volume of the metastasis. All these parameters will be correlated with the CNS toxicity.

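### Baseline brain-metastasis status at lorlatinib start has no option for unknown or not imaged, so the stratum without brain metastases can mix imaged-negative and unimaged patients

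*Protocol*

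**What the plan says.** Protocol Section 9.3 lists the pre-treatment variables. Three consecutive rows matter:

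- "Brain metastasis at diagnosis" may be answered Yes, No or Unknown.
- The imaging method used to screen for brain metastases may be "CT/MRI/None/Unknown".
- "Brain metastases present at time of lorlatinib initiation" may be answered Yes or No only.

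The third row matches the baseline by which three effectiveness endpoints are split in the objectives table of Section 9.1: rwPFS, cumulative incidence of brain metastases, and "Real world Time to intracranial progression rate at 12 and 18 months with and without brain metastasis at baseline".

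On whether a baseline scan exists, the schedule in Section 9.2 marks "Assessments brain MRI" at the baseline visit, and the imaging text in Section 9.3 says "Brain MRI will be collected at baseline and in case of CNS toxicity". That imaging text stands under the exploratory variables, for which 30 patients are expected, and the same part of the section says: "The study will capture results/data only from procedures that were actually performed as part of a participant's routine medical care". Section 9.2.1 does not make brain imaging a condition of entry.

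**The concern.** The protocol foresees patients with no screening imaging, and it foresees unknown status at diagnosis. It drops that possibility on the one field that describes status at the index date. A No can then mean a negative scan or no scan at all.

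The stratum without baseline brain metastases is meant to show how often the brain becomes involved during first-line lorlatinib in patients who start free of it. If it contains unimaged patients, a lesion first seen on a later scan may be prevalent disease counted as a new event. Equally, an unimaged patient who is never scanned may add follow-up time without any chance of an event. Either way the reported 12- and 18-month figures no longer describe the population named in the endpoint.

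**Working it through.** The plan states no figure for unimaged patients or for brain-metastasis rates, so there is none to reproduce. The check has two parts: the passages side by side, then an illustration of size and direction.

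**Can the protocol's own fields separate the two groups?** Only in part. The screening-method row identifies patients recorded as None or Unknown. It has no date, however, and it directly follows the row on status at diagnosis. Criterion 7 of Section 9.2.1 admits patients who relapsed after early-stage disease, and Section 9.3 distinguishes de novo from relapsed disease. For a relapsed patient, an entry of MRI may describe a scan made well before lorlatinib. Such a patient looks screened but may have had no brain imaging near the first dose. An analysis plan cannot recover a date that was never collected.

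**Inputs for the illustration**

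- N = 116 (Section 9.5).
- Prevalence q = 35/149 = 0.235. Section 7 gives 35 lorlatinib patients with baseline brain metastases in the pivotal phase III trial and 149 treated with lorlatinib. Applying this share to this cohort, and to its unimaged patients, is an assumption.
- Unimaged share u = 5%, 10% or 20%: assumed, since the protocol gives no value.
- All unimaged patients are recorded as No: assumed, as the worst case.

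**Misclassified share.** Unimaged U = 116 × u. Occult cases O = U × 0.235. Imaged negatives S = (116 − U) × 0.765. Recorded stratum = S + U. Misclassified share = O / (S + U).

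| u | U | O | S | S + U | O / (S + U) |
|---|---|---|---|---|---|
| 5% | 5.8 | 1.4 | 84.3 | 90.1 | 1.5% |
| 10% | 11.6 | 2.7 | 79.9 | 91.5 | 3.0% |
| 20% | 23.2 | 5.5 | 71.0 | 94.2 | 5.8% |

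If occult prevalence among the unimaged were 10% instead, the last column would be 0.6%, 1.3% and 2.5%.

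**Direction.** Let r be the true event rate in patients without brain metastases, d the share of occult cases later counted as events, and s the relative detection of events in unimaged patients who are truly negative. Then:

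observed rate = [S × r + (U − O) × r × s + O × d] / (S + U)

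Take r = 3% (assumed).

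| u | d = 1, s = 1 (every occult lesion later counted) | d = 0, s = 0 (unimaged patients never scanned) |
|---|---|---|
| 5% | 4.5% | 2.8% |
| 10% | 5.9% | 2.6% |
| 20% | 8.6% | 2.3% |

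For u = 10%, the upper case is (79.9 × 0.03 + 8.9 × 0.03 + 2.7) / 91.5 = 5.9%, and the lower case is (79.9 × 0.03) / 91.5 = 2.6%. If occult cases are counted at the same rate as true negatives (d = 0.03, s = 1), the observed rate stays at 3.0%. With r = 10% the corresponding ranges are 9.4% to 11.4%, 8.7% to 12.7% and 7.5% to 15.2%. The sign of the bias depends on follow-up imaging, which the protocol leaves to routine practice: the schedule in Section 9.2 marks brain MRI at baseline only, and later response assessment may use CT, MRI or other methods.

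**The case against.** The strongest reply is that the variable table lists answer options and nothing more. A reader might infer that unimaged patients are forced into No. The protocol does not say so: the field is not declared mandatory, it could be left blank, and eCRF queries await a data management plan (Section 9.6). Section 9.7 leaves outcome definitions and missing-data methods to the SAP, and the screening-method row lets a SAP set aside patients recorded as None or Unknown. This stands, and it is why the point says only that such patients may be recorded as No. It does not close the gap. A blank does not distinguish not imaged from not entered, and the undated screening row does not show who was imaged near the first dose.

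A second reply is that few patients may be affected. Baseline MRI is in the schedule, and the sites are highly specialised hospitals. That is plausible, and nothing in the protocol supports any particular unimaged share.

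A reader might also infer that event rates in this stratum are inflated. The documents do not support a direction. Inflation needs occult lesions to be scanned later and called new or progressing. Section 7 describes lorlatinib as crossing the blood-brain barrier, so some occult lesions may respond and never be counted, and patients not scanned at baseline may stay unscanned.

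Finally, these are secondary endpoints of a descriptive safety study. That is correct and limits the weight of the point.

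**Conclusion.** The point holds as a flaw in a variable definition. The field that describes brain-metastasis status at the index date cannot separate imaged-negative from unimaged patients, although the protocol foresees the latter and does not require baseline brain imaging. Three secondary effectiveness endpoints are affected; the primary adverse-event objective is not.

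The size cannot be derived from the protocol. The misclassified shares of 1.5%, 3.0% and 5.8% are upper bounds. They rest on assumed unimaged shares of 5%, 10% and 20%, an assumed occult prevalence of 23.5%, and every unimaged patient being recorded as No. They should not be read as points added to the event rate, because the bias can run either way. This is a cheap improvement that should be made before much data has been entered, since imaging dates are harder to reconstruct later.

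**What to change.** In Section 9.3:

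- Add an answer for unknown or not imaged to the status-at-initiation variable.
- Collect the date and modality of the last brain imaging before the first dose.
- Define the stratum without baseline brain metastases as imaged and negative.

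In the analysis, report unimaged patients as a separate group, with a sensitivity analysis that counts them as negative. No additional scan is needed, so the non-interventional character of the study is unchanged.

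The cost is one response option, a date field and a modality field. The stratum without brain metastases would also shrink by the unimaged patients, about 6 to 23 under the assumptions above (for example from 91.5 to 79.9 expected patients at 10% unimaged), with some loss of precision.
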